5.0 Inclusion and Exclusion Criteria/ Study Population

Age ranges were chosen based on previous published and unpublished studies performed in our laboratory indicating that a significant decrease in pneumococcal vaccine response starts to appear at age 65 and that prior to age 50 the response is similar to individuals 20-30 age of years, i.e. optimal range. We chose the 35-45 age group specifically, and not 20-30, as renal transplants recipients with cause of renal failure is type II diabetes or hypertension are well represented in the MUSC transplant population.

Individuals will be screened for eligibility depending on the group they are recruited for:

Group 1 Older RT group (Age 65-75)

Group 2 Younger RT group (Age 35-45)

The elderly (65-75 years) and young (35-45 years) renal transplant recipient groups 1 and 2 seen at the MUSC and VA transplant clinics whose end-stage renal disease was caused by hypertension (HTN) and/or DM II who are at least 1 year post-transplant and due for their PCV 13 vaccination will be asked to participate in the study. Those that do not wish to participate in the study will receive the clinical standard of care.

Group 3 Individuals with DM II and/or HTN age 65-75.

Individuals with the diagnosis DM II and/or HTN due for routine visits at the general internal medicine or endocrinology clinic at the Ralph H Johnson VA Medical Center will be screened for normal (Glomerular filtration rate \geq 60) versus abnormal (GFR $<$ 60) who are due for their standard of care PCV13 vaccine will be asked to participate.

Group 4: 65-75 years old without DM2 or renal impairment who are due for their standard of care vaccination with PCV13.

Group 5: Healthy persons 35-45 years of age without DM or renal impairment willing to participate in a study to receive PPV23, if they have not received this previously or/and PCV13, at least 1 year after PPV23 vaccination.

Inclusion/Exclusion criteria

Inclusion criteria are group specific. HBV, HCV and HIV testing are not necessary in the RT groups as all RT recipients are tested prior to transplant.

Exclusion criteria are either applicable to all groups or group specific. Therefore we have listed the exclusion criteria applicable to ALL groups first. Group specific criteria are listed under each group

Exclusion Criteria common to all groups

1. Previous immunization with PCV13.

2. Pregnancy, no contraceptive practice in women of childbearing age, or breastfeeding
3. Known anaphylaxis, hypersensitivity or “bad allergic reaction” to the pneumonia vaccine. This does not include egg allergy or previous Guillan Barre syndrome.
4. Those who received blood products or gamma globulin within 3 months.
5. Inability to comprehend or sign the informed consent form
7. Previous/present illness that may affect immune response to the vaccine (previous pneumococcal Disease, removal of the spleen, auto-immune disease such as lupus or rheumatoid arthritis, end-stage liver disease, or cancer)
8. Significant abnormalities (3xULN and all those considered to be critical values) in CBC, chemistries including glucose.
9. HIV, HBsAg or HCV positivity
10. Receipt of PPV23 within 1 year

Groups 1 (65-75 yrs) and 2 (35-45 yrs) Renal Transplant populations

Inclusion Criteria:

Age range; RT 35-45 or 65-75 years old,
 End stage renal disease cause either DM2 and/or hypertension (HTN)
 Renal transplant >12 months ago
 We will not restrict volunteers with respect to gender, ethnic or racial group.

Exclusion criteria:

1. Medications that are known to affect immune function (chemotherapy, anti-TNF α agents) with the exception of anti-rejection medication.
 2. Episode of acute rejection within the last 6 month period
- The inclusion/exclusion criteria will be determined by chart review and pregnancy test for females of child bearing potential.

Group 3: Diabetic/hypertensive 65-75 year old controls

Inclusion Criteria

65-75 years old with DM2 and/or HTN.
 Previous immunization with PPV23 >1 year prior
 Willingness to be tested for HIV, HBV and HCV
 “normal kidney function” defined as glomerular filtration rate (GFR) of 60% or above
 We will not restrict volunteers with respect to gender, ethnic, or racial group.

Exclusion Criteria

1. Medications that are known to affect immune function (chemotherapy, anti-TNF α agents).

The inclusion/exclusion criteria will be determined by chart review.

Group 4: Healthy Control 65-75 yr old

Inclusion Criteria

65-75 years old without DM2. May have high blood pressure (systolic>140 and/or diastolic>90) as long as it is well controlled (systolic<140 and/or diastolic <90) and has not affected kidney function.
 Previous receipt of PPV23 > 1 year prior
 Willingness to be tested for HIV, HBV and HCV
 We will not restrict volunteers with respect to gender, ethnic, or racial group.

Exclusion Criteria

6. Medications that are known to affect immune function (chemotherapy, anti-TNF α agents).

The inclusion/exclusion criteria will be determined by chart review and pregnancy test for females of child bearing potential.

We will not restrict volunteers with respect to gender, ethnic, or racial group.

Group 5: Healthy Control 35-45 yr old

Inclusion Criteria

35-45 years old without DM2. May have high blood pressure (systolic>140 and/or diastolic>90) as long as it is well controlled (systolic<140 and/or diastolic <90) and has not affected kidney function.

Willingness to be tested for HIV, HBV and HCV and filling out a medical questionnaire that will include diabetes screening.

We will not restrict volunteers with respect to gender, ethnic, or racial group.

Exclusion Criteria

6. Medications that are known to affect immune function (chemotherapy, anti-TNF α agents).

The inclusion/exclusion criteria will be determined by chart review and pregnancy test for females of child bearing potential.

Diversity: we will attempt to mimic the local renal transplant recipient population consisting of a disproportionately high number of males (>60%) of African-American decent, \pm 50%. This gender and race pattern of distribution is consistent with the patient population of the Ralph H. Johnson VA Medical Center outpatient clinics, where we will be recruiting most of our control populations (Groups 3-5). We therefore anticipate a diverse population as a result of eligibility at the recruitment sites.

Children will NOT be included in this study as this study is uniquely aimed at defining the immune response to PCV13 in ADULTS. The immune response to PCV13 is age-dependent and therefore completely different in children, as is the recommended vaccine frequency.

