15.0 Risks to Subjects

Risks to subjects are minimal. This study involves immunization with an FDA approved vaccines which are standard of care for all study groups included with the exception of the young healthy group. Small volume blood draws will be performed at various time points before and after vaccination as outlined above. The risks associated with blood draws is minimal and may result in minor hematomas at the blood draw site and/or bleeding. The blood samples, lymphocytes and cDNA will **not** be marked with donor identifiable data. The risk of breach of confidentiality is minimal, all staff associated with the project have completed appropriate training in human subject research regulations and policies (including the Health Information Portability and Accountability Act (HIPAA)).

We will obtain IRB approval at the VA/ MUSC in compliance with Federal Regulations, state and local laws and institutional policy governing human subject research. Following informed consent, all volunteers who choose to participate in this research will complete a questionnaire to evaluate their overall health and eligibility. The vaccination protocol and blood draw schedule will be explained in detail. The risks of blood draws and vaccination with the conjugated pneumococcal polysaccharide vaccine will be explained and the intent to isolate their lymphocytes for the use in flow cytometry and other molecular biology experiments for further study will be outlined as part of the informed consent process prior to any specimens being obtained.

Possible side effects of blood draws (approximately 60 mL/visit) may be the risk of pain, small bruises and bleeding, or infection. All blood draws will be done by experienced technicians or an experienced medical doctor under sterile conditions with proper measures to prevent risks and pain. There are no long term risks associated with blood draws.

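### The transplant groups (1 and 2) can admit people never given PPV23, so the transplant contrast may also carry a difference in vaccine priming

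*Combined protocol and SAP*

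**What the plan says.** For Groups 1 and 2, the inclusion list in Section 5.0 gives an age range, end-stage renal disease from DM2 and/or hypertension, and "Renal transplant >12 months ago", plus a statement that sex, ethnicity and race are not restricted. PPV23 does not appear. The recruitment text in the same section invites recipients "who are at least 1 year post-transplant and due for their PCV 13 vaccination will be asked to participate in the study". The only PPV23 rule that reaches them is common exclusion 10: "Receipt of PPV23 within 1 year".

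The other groups are handled differently. Group 3 must have "Previous immunization with PPV23 >1 year prior" and Group 4 must have "Previous receipt of PPV23 > 1 year prior". Group 5 volunteers must be willing "to receive PPV23, if they have not received this previously or/and PCV13, at least 1 year after PPV23 vaccination". Section 10.0 gives PPV23 on day 0 to Group 5 members who have never had it, with PCV13 on day 366.

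Section 10.0 explains the Group 5 dose as the means of ensuring that everyone in the study had PPV23 at least a year before PCV13. Section 15.0 states that Groups 1-4 will all have had PPV23 already through ordinary care, and describes the matching step in Group 5 as indispensable for interpretable data.

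**The concern.** Only in the two transplant groups is earlier PPV23 neither required nor supplied. The protocol relies on a common vaccine sequence across all five groups, but for the groups of main interest it asserts that sequence without checking it.

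Specific Aim 1 (Section 1.0) uses Group 1 versus Group 3 for the transplant component and Group 1 versus Group 2 for the age component, with Groups 4 and 5 as healthy references. If some transplant recipients have never had PPV23, then Group 1 versus 3, Group 1 versus 4 and Group 2 versus 5 each compare a partly unprimed group with a fully primed one. Part of any difference, or part of a missing difference, could then come from vaccination history and not from transplantation. Group 1 versus 2 is affected only if the unprimed share differs by age.

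The problem could also be hard to see afterwards. PPV23 history is not named in the list of data to be collected in Section 10.0 and is not a term in the Section 12.0 model.

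**Working it through.** **1. Who can receive PCV13 without earlier PPV23 (Sections 5.0 and 10.0)**

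| Group | Earlier PPV23 required | PPV23 supplied on study | Unprimed entry possible |
|---|---|---|---|
| 1, 2 | No | No | Yes |
| 3, 4 | Yes, more than 1 year before | No | No |
| 5 | No | Yes, if never received | No |

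Common exclusion 10 does not change the first row, because a person never vaccinated has not been vaccinated within a year. Being due for PCV13 does not imply earlier PPV23 either: Section 1.0 describes a recommended regimen containing both vaccines and states no order.

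**2. The plan's own figures (Section 12.0)**

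- Significance level: five groups give 5 x 4 / 2 = 10 pairs, and 0.05/10 = 0.005, as stated.
- Correlation power, n = 200, r = 0.20: atanh(0.20) x sqrt(197) - 1.96 = 0.885, so power is 81.2% (stated: above 80%). The 95% interval half-width at r = 0 is tanh(1.96/sqrt(197)) = 0.139 (stated: 0.14).

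These reproduce, but the present point does not depend on them. The effect-size figure for the group comparisons is not shown in the text available.

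**3. Inputs for the size of the bias**

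- From the documents: two-sided alpha 0.005, 80% power and within-subject correlation 0.5 (Section 12.0). Group size is 40 (Section 12.0) or 275/5 = 55 (Section 6.0; Table 2 in Section 10.0 also runs to subject 55). Both are shown.
- Assumed: unprimed share p = 10-20% and unprimed-versus-primed difference d = 0.5-1.0 SD. The documents give neither figure, nor the sign of d.

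**4. Bias**

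If the primed mean in Group 1 is m, the mixed mean is (1 - p)m + p(m + d) = m + pd. Group 1 minus Group 3 is therefore the transplant effect plus p x d. This runs from 0.1 x 0.5 = 0.05 SD to 0.2 x 1.0 = 0.20 SD, and is 0 when p = 0. For Group 1 versus 2 it is (p1 - p2) x d.

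**5. Detectable difference**

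The normal approximation is (2.807 + 0.842) x sqrt(2/n), which gives 0.816 SD at 40 and 0.696 SD at 55. The noncentral t gives 0.837 and 0.709 SD. These apply at a single time, and also to change, whose SD is sqrt(2 x (1 - 0.5)) = 1. The bias is then 6-24% of the detectable difference at 40 per group and 7-28% at 55.

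The Section 12.0 model lists group and time without an interaction, so its group contrast averages the two times. Its SD is sqrt((1 + 0.5)/2) = 0.866, and the detectable difference is 0.725 or 0.614 SD. If d took the same values on that contrast, the shares would be 7-28% and 8-33%.

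**6. Effect on the test**

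Simulation with 400,000 runs, a naive/primed mixture in one group, and a t-test at 0.005. False positives assume no true transplant effect. Power is for a true effect of the detectable size that the bias opposes.

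| p, d (SD) | False positives, n = 40 | n = 55 | Power, n = 40 | n = 55 |
|---|---|---|---|---|
| 0, 0 | 0.49% | 0.50% | 79.9% | 80.0% |
| 10%, 0.5 | 0.60% | 0.64% | 72.8% | 71.3% |
| 10%, 1.0 | 0.90% | 1.07% | 63.2% | 60.2% |
| 20%, 0.5 | 0.92% | 1.10% | 64.6% | 61.6% |
| 20%, 1.0 | 2.42% | 3.41% | 44.7% | 38.7% |

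Outside this grid, at 40 per group, p = 5% with d = 0.3 SD gives 0.51% false positives and 78% power. At p = 50% with d = 0.8 SD, a normal approximation gives 13.9% false positives.

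**The case against.** The strongest reply is that Section 15.0 already answers the point: Groups 1-4 are said to have had PPV23. Nothing in the documents says that unprimed recipients will be enrolled, and if the statement is true there is no bias. The transplant criteria are also shorter elsewhere because of pre-transplant care (Section 5.0 waives HIV, HBV and HCV testing for that reason), so the missing line may follow the same logic. This stands as an explanation of intent. But the statement is an expectation, not an eligibility check. It covers Groups 3 and 4 equally, and there the sponsor still wrote the criterion. The waiver for viral testing does not mention PPV23.

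Second, p and d are assumptions, and the worst figures come from one corner of the grid. That is right: the calculation shows what could happen and does not show that harm is likely.

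Third, the data list in Section 10.0 also leaves out items that must be known, such as age and vaccination date, so its silence does not prove that PPV23 history goes unrecorded. This also stands. The silence is a reason to name the field and no more. Likewise, the lack of a PPV23 term in the model is no defect if everyone is primed.

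Fourth, a requirement of more than one year would not equalise the interval since PPV23, or whether it came before or after transplant. True: it removes only the primed-versus-unprimed imbalance.

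**Conclusion.** The concern holds. The Groups 1 and 2 criteria, as written, allow entry that breaks a premise on which the protocol says interpretation depends. Confidence in the omission is high. The size of any effect is unknown, because neither the unprimed share nor its effect is given, and its direction cannot be stated.

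If Section 15.0 is correct the bias is zero. Under the assumed ranges, false positives on Group 1 versus 3 rise from 0.5% to at most 2.4% (40 per group) or 3.4% (55). If the bias opposes a real effect, power falls from 80% to as low as 45% or 39%. At the mild end the change in error rate is negligible. The point should be fixed, but it is not fatal to the design.

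**What to change.** Reconcile the Groups 1 and 2 criteria with Sections 10.0 and 15.0. One way is to carry over the protocol's own Group 3 line. If the sponsor does mean to admit recipients without earlier PPV23, the statements in Sections 10.0 and 15.0 need correcting instead. That choice is the sponsor's.

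In either case, add PPV23 receipt (yes/no) and date of last dose to the Section 10.0 data list for all groups. If unprimed recipients are already enrolled or will be admitted, report their number by group and repeat the main contrasts without them as a sensitivity analysis. Leave the primary model unchanged.

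The cost is small: one eligibility line or a text correction, and two fields. Exclusion 10 already obliges staff to establish PPV23 history, and the means are in place. For Groups 1 and 2, "The inclusion/exclusion criteria will be determined by chart review and pregnancy test for females of child bearing potential", and under Section 15.0 "all volunteers who choose to participate in this research will complete a questionnaire to evaluate their overall health and eligibility".

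The downside of the eligibility line is that some recipients may be screened out. The documents give no coverage or screening figure, so the number is unknown; under Section 15.0's own premise it is none. The sensitivity analysis loses a little precision. Dropping 10% or 20% of one group raises the detectable difference from 0.84 to 0.86 or 0.89 SD at 40 per group (36 or 32 versus 40), and from 0.71 to 0.73 or 0.75 SD at 55 (49-50 or 44 versus 55).

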1.0 Objectives / Specific Aims

Normal aging is characterized by changes in the immune system that result in increased susceptibility to infections, poor response to new vaccine antigens, loss of protection offered by previous vaccinations and decreased immune surveillance [1, 2]. Despite the chronic inflammation associated with immunosenescence, the aging population is living longer. Consequently, individuals >65 years of age, are the most rapidly growing population amongst those with end stage renal disease (ESRD) and account for more than 18% of renal transplant (RT) recipients [3].

The incidence of pneumococcal disease is significantly higher in both elderly [4] and those with RT [5] and the combination of these factors is likely additive, if not synergistic, for invasive pneumococcal disease (IPD). It is recommended that both elderly >65 and RT recipients be vaccinated with a regimen that includes both the 13-valent pneumococcal conjugate vaccine (PCV13) and the 23-valent pneumococcal polysaccharide vaccine (PPV23). However, small immunogenicity studies performed in the transplant populations have not shown superiority of a PCV containing regimen [6, 7]. Moreover, the addition of PCV to the pneumococcal vaccine regimen does not improve protective immunity in this population. Studies to date fail to elucidate the possible foundation of the disappointing immune responses to the PCV regimens, data essential for the development of a rational and effective next generation pneumococcal vaccine.

Specific Aim 1.

We will **define immune responses by measuring** serum antibody and functional antibody responses to PPS 14, 19A and 23F following PCV13 vaccination in RT recipients 65-75 years of age and compare these to: RT recipients 35-45 years of age and persons with DM/HTN but normal function 65-75 years of age to dissect out the age and RT components respectively. Healthy persons 35-45 and 65-75 years of age will be studied as age appropriate reference.

Specific Aim 2.

We will measure and characterize the antigen-specific B cell subset response following immunization with PCV13 in the RT recipients 65-75 years of age and compare them to each of the groups described in Specific Aim 1 using flow cytometry and fluorescently labeled PPS and monoclonal antibodies. These measures will be correlated with post-immunization functional antibody activity, a surrogate of protection.

Specific Aim 3.

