Accordingly, pneumococcal vaccination is recommended for all adults ≥ 65 years of age and all RT recipients [12, 13]. In 2012 the vaccination recommendations by the Advisory Committee on Immunization Practices (ACIP) for these immune compromised adults, were changed to include vaccination with the 13-valent pneumococcal conjugate vaccine (PCV13) [12]. Although highly successful in infants, immunogenicity studies have overall failed to demonstrate superiority of PCV based regimens in older adults [14]. Similarly, a prime-boost regimen based on sequential immunization with PCV7 and the 23-valent pneumococcal polysaccharide vaccine, Pneumovax[®] (PPV23), has not demonstrated improved responses in RT and liver transplant populations [6, 7]. The RT population ≥ 65 years of age is rapidly growing and represents a unique subpopulation with combined immunodeficiencies related to aging [15] and immunosuppressive drugs related to transplant. Both aging and RT result in a marked increased risk of pneumococcal disease with decreased immune response to pneumococcal vaccination. The immune response to vaccination with PCV is poorly characterized in the aging and transplant populations, and may not be more effective than PPV23 alone, implying the need for alternate vaccine/adjuvant strategies. Moreover, studies characterizing and comparing antigen-specific B cell responses in well-defined RT populations are lacking.

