We have developed directly labeled fluorescent PPS to enumerate and characterize PPS-specific B cells. This allowed the analysis of antigen-specific B cell responses to pneumococcal vaccination. The results of these studies demonstrated that the immune response to PPV in young adults consists predominantly of IgM memory B cells [16]. In contrast, in the elderly who are deficient in memory B cells, particularly IgM memory B cells [17], the predominant B cell phenotype in response to PPS consists of switched memory B cells (IgG/A+IgM-CD27+)[18]. HIV+ individuals, are also deficient in CD27+IgM+ B cells yet the predominant response consists of PPS-specific CD27+IgM+ B cells [19-22], albeit at significantly reduced numbers. Thus, the cause of poor pneumococcal vaccine responses varies according to study population. Several investigators and our preliminary data show that like the elderly and HIV-positive, absolute number and percentage of memory B cells are significantly lower in stable RT recipients, at 6 months to 5 years post-RT, compared to healthy subjects [23, 24]. Moreover, low number and percentage of IgM memory B cells correlate with poor antibody responses to PPV23.

This may however not be the only cause for poor vaccine responses. The ability to isolate antigen-specific B cells allows us to explore other deficits and/or changes in surface markers and gene expression potentially implicated in poor vaccine responses. It has been well described that members of the TNFR family and

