The vaccine(s) administered to the participants are FDA approved vaccinations and vaccination protocols. The standard and recommended dose of vaccine will be administered either by a qualified nurse or physician and both vaccines are considered low risk. In groups 1-4 PCV13 will be administered per standard of care and is not part of the experimental protocol. In group 5, both PPV23 and PCV 13 are not routine part of care and are part of the experimental protocol. These vaccines have however been extensively studied in this and other populations and are considered low risk and 70-80% protective against pneumococcal disease [30].

The risk associated with blood draws is minimal.

The data to be collected will be stored using an excel spread sheet. The data include:

-cause of end stage kidney disease if applicable

Date of kidney transplant

Complete blood count (CBC), comprehensive chemistry profile including renal and liver functions, HbA1c, serum albumin as measure of nutrition, HbsAg, HCV and HIV test

Pre- and post-immunization serum antibody titers and opsonophagocytic antibody titers to PPS14, 19A and 23F in ug/mL

IgM and switched memory B cell number and percentage

PPS+ B cell number and percentage

Serum BAFF concentration

Gene expression of the genes listed below in Table 4

#	GENE SYMBOL	GENE TITLE	PROTEIN FUNCTION	#	GENE SYMBOL	GENE TITLE	PROTEIN FUNCTION
Apoptosis				Lymphocyte signaling			
1	Bcl-2	B-cell lymphoma 2	Apoptotic suppressor	30	CBLB	E3 ubiquitin-protein ligase	Negatively regulates B cell Ag receptor signaling
2	Bcl-Xl (BCL1)	B-cell lymphoma-extra large	Apoptotic suppressor	31	FCRL2	Fc receptor like 2	Expressed in memory B cells in humans
3	Mcl-1	Induced myeloid leukemia cell differentiation protein Mcl-1	Apoptotic suppressor	32	CD1D	CD1D	Antigen presentation
4	BAX	BCL2-associated X protein	Pro-apoptotic function	33	CD200	OX2 membrane glycoprotein	Controls inflammation; immunosuppression
5	BAD	BCL2-associated agonist of cell death	Pro-apoptotic function	34	LAIR1	Leukocyte associated immunoglobulin like receptor 1	Inhibitor of B cell mediated signaling
6	BIM (BCL11)	BCL2-interacting mediator of cell death	Pro-apoptotic function	35	CD72	B cell differentiation antigen CD72	Negative regulator of B cell responsiveness
7	FAS	Fas cell surface death receptor	Apoptosis signaling	36	RFTN1	Raft linking protein	B cell antigen receptor mediated signaling

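### The Group 1 versus Group 2 contrast is read as the age component, but anti-rejection regimen is not a listed data item and neither regimen nor time since transplant enters a stated analysis

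*Combined protocol and SAP*

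**What the plan says.** Section 1.0 (Specific Aim 1) compares RT recipients aged 65-75 with RT recipients aged 35-45, and with people aged 65-75 who have diabetes or hypertension, "to dissect out the age and RT components respectively". The first of these comparisons, Group 1 versus Group 2, is therefore the plan's age contrast among recipients.

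For both RT groups, section 5.0 requires "Renal transplant >12 months ago". The population text in the same section also gives only a minimum. The immune-drug exclusion reads "Medications that are known to affect immune function (chemotherapy, anti-TNF α agents) with the exception of anti-rejection medication", with no drug class, number or dose specified. Recent acute rejection (within 6 months) is excluded.

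Section 2.0 says that the older RT population "represents a unique subpopulation with combined immunodeficiencies related to aging [15] and immunosuppressive drugs related to transplant". It reports the supporting memory B-cell findings in "stable RT recipients, at 6 months to 5 years post-RT".

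The data list in section 10.0 includes cause of kidney failure and "Date of kidney transplant". It does not include anti-rejection regimen.

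In section 12.0, the linear mixed model for Aims 1 and 2 has fixed effects for group and time and a random subject effect. The Aim 3 model adds response status. Neither contains regimen or time since transplant, and no matching or stratification on them is described.

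**The concern.** Groups 1 and 2 are defined by age and not randomised, so they can differ in anything that goes with age in a transplant clinic. The protocol calls the RT population heterogeneous, but its response is to restrict the cause of kidney failure. It does not restrict or adjust for the drugs that it names as a source of the deficit.

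If the two groups differ in regimen or in years since transplant, and that factor affects the vaccine response, the group coefficient absorbs the difference and the report calls it age. The distortion could create an age effect or hide one. The same contrast is carried into the B-cell results of Aim 2 and the receptor results of Aim 3.

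The point is confined to Group 1 versus Group 2. In Group 1 versus Group 3 the drugs are part of what being a transplant recipient means, so they do not confound that contrast in the same way.

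**Working it through.** **The plan's own figures.** The detectable group differences are in Figure 7, which is not available to read. The figures given in the text of section 12.0 reproduce:
- Power for r = 0.20 with 200 subjects: Φ(atanh(0.20)·√197 − 1.96) = 81.2%, against a stated figure above 80%.
- Half-width of the 95% interval at r = 0: tanh(1.96/√197) = 0.139, against ±0.14.
- Bonferroni level: five groups give 10 pairs, and 0.05/10 = 0.005.

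These figures neither support nor weaken the point. They only fix n = 40 per group and the two alpha levels used below.

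**Detectable Group 1 versus Group 2 difference.** The formula is (z₁₋α/₂ + z₀.₈₀)·√(2/n), with n = 40, 80% power and a two-sided test.
- α = 0.05: (1.960 + 0.842) × 0.2236 = 0.63 SD (0.634 by noncentral t).
- α = 0.005: (2.807 + 0.842) × 0.2236 = 0.82 SD (0.84 by noncentral t).

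With the plan's within-subject correlation of 0.5, the SD of a change score is √(2 × (1 − 0.5)) = 1 times the single-time SD. The same figures therefore apply to a comparison of changes.

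**Possible distortion.** Bias = difference in prevalence of the factor × effect of the factor in SD. The documents give neither input, so both ranges are assumptions: 20 to 30 points, and 0.5 to 1.0 SD. With no true age effect, the false-positive rate is P(|Z + bias/√(2/n)| > z₁₋α/₂), at n = 40:

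| Imbalance | Effect of factor | Bias | α = 0.05 | α = 0.005 |
|---|---|---|---|---|
| 0.20 | 0.5 SD | 0.10 SD | 7.3% | 1.0% |
| 0.30 | 0.5 SD | 0.15 SD | 10.3% | 1.7% |
| 0.20 | 1.0 SD | 0.20 SD | 14.5% | 2.8% |
| 0.30 | 1.0 SD | 0.30 SD | 26.9% | 7.1% |

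With no imbalance the bias is zero. A larger sample does not reduce the bias. At 55 per group (275/5, from section 6.0), the 0.30 SD case gives 35.0% and 10.9%.

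**Cost of adjustment.** The variance of the contrast is multiplied by 1/(1 − R²), where R² is from group regressed on the covariate. The figures below are at n = 40, α = 0.005 and 80% power, from a base of 0.82 SD.
- One binary factor with average prevalence 0.5: R² equals the squared imbalance. At 20 points the multiplier is 1/(1 − 0.04) = 1.042, giving 0.83 SD. At 30 points it is 1/(1 − 0.09) = 1.099, giving 0.86 SD.
- Time since transplant, with group means d SD apart: R² = (d/2)²/(1 + (d/2)²). For d = 0.25, 0.5 and 1.0 the multipliers are 1.016, 1.062 and 1.25, giving 0.82, 0.84 and 0.91 SD.

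No credit is taken for outcome variance that the covariates explain.

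**The case against.** The strongest reply is that nothing in the documents shows Groups 1 and 2 to differ in regimen or duration. That is correct. A reader might infer that the age contrast is biased; the documents support only that it is unprotected. A 35-45 year old may have fewer possible years since transplant, but that is an argument about maxima and does not establish how the enrolled groups are distributed.

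A reader might also infer that missing regimen data could never be recovered. The documents point the other way. Section 5.0 decides RT eligibility, including the medication criterion, by chart review. Section 11.0 leaves the code link with study personnel. Section 16.0 allows clinical information to be joined to the results at analysis if needed. The data list in section 10.0 may also not be exhaustive, since it omits basic items such as age and sex. What stands is that regimen is not a listed item, and that an ad hoc look-up is neither a uniform day-0 record nor a pre-specified adjustment.

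A third tempting inference is that eligibility is wrong. Exempting anti-rejection drugs is close to unavoidable in a transplant cohort. The 6-month to 5-year range describes earlier B-cell findings and is not an eligibility standard.

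Existing features help in part. The 12-month minimum, the rejection exclusion and the restriction on cause of kidney failure narrow the variation. Group 4 versus Group 5 gives an age comparison free of transplant drugs. None of these separates age from regimen among recipients.

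Finally, regimen may be chosen partly because of age. Adjustment then changes the question from the total effect of age to the part that does not act through regimen. That is a reason to report the adjusted contrast beside the planned one and not in its place.

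**Conclusion.** The point holds as a gap in data collection and analysis. Followed as written, the plan would label any regimen or duration difference between Groups 1 and 2 as age, although it names anti-rejection drugs as a cause of the deficit and already collects transplant date.

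The size is unknown. The illustrative 0.10 to 0.30 SD rests wholly on assumed imbalances and drug effects. It is about 16% to 48% of the difference detectable at alpha 0.05 (0.10/0.63 to 0.30/0.63) and 12% to 37% at alpha 0.005 (0.10/0.82 to 0.30/0.82). That is enough to matter for interpretation. It does not show that a finding would be spurious. The change is worth making because it is cheap, not because bias has been demonstrated.

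**What to change.** 1. Add day-0 anti-rejection regimen to the section 10.0 data list for Groups 1 and 2: drug classes, and any B-cell-depleting therapy with its date. Take it from the chart review that already determines eligibility.
2. Tabulate regimen and years since transplant by group.
3. For Aims 1 and 2, pre-specify a separate model in RT recipients only, with the Group 1 versus Group 2 contrast adjusted for time since transplant and a coarse regimen class. It must be separate because these covariates are undefined for Groups 3 to 5. Report it as a sensitivity analysis beside the planned unadjusted contrast.
4. For Aim 3, with 10 participants per group, describe these factors only. The sample cannot carry the extra terms.
5. State in advance that if the contrast changes materially on adjustment, it will not be attributed to age alone.

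The cost is a few chart fields, a small loss of degrees of freedom (more if regimen has several levels) and slightly lower precision. At alpha 0.005 the detectable difference goes from 0.82 SD to 0.83-0.86 SD for one binary factor with an assumed 20 to 30 point imbalance. Eligibility and treatment do not change.
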